12 SAFETY ANALYSIS

The safety analyses will be performed using the safety population. In general, safety analyses will be presented by gene mutation (e.g., BRCA1/2, ATM, CDK12, CHEK2, and Other) and Overall. Safety data may also be presented by measurable disease status at baseline to explore the safety profile between patients with and without measurable disease at baseline. Additionally, safety data will be further explored by age group (< 65, 65-74, ≥ 75) and race (White, Other).

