Sandhu et al. reported on a cohort of 4 patients with germline BRCA2-mutant advanced prostate cancer treated with either olaparib (3 patients) or niraparib (1 patient).⁴² In the patients treated with olaparib, PSA and radiological responses lasting 34 and 26 months were noted in 2 patients, and SD of 10 months was noted in the 3rd. The patient treated with niraparib demonstrated primary resistance and quickly progressed; the total duration for niraparib treatment in that patient was 6 weeks.

Olaparib was further evaluated in mCRPC in several Phase 2 studies. In one trial that enrolled multiple tumor types, Kaufman et al. (2014) reported efficacy data for 8 BRCA mutant mCRPC patients who had received a median number of 2 prior therapies.⁴³ All patients had experienced disease progression following hormonal therapy; 75% had received prior docetaxel, and 50% had received prior platinum (carboplatin or cisplatin). Four patients had a confirmed PR (confirmed RECIST ORR=50%) and 2 patients (25%) had a best response of SD. Overall duration of response was 327 days, PFS was 7.2 months and median OS was 18.4 months.

More recently, olaparib demonstrated compelling clinical activity in a Phase 2 open-label investigator-sponsored study⁹ evaluating mCRPC patients with evidence of HRD. In the Trial of PARP Inhibition in Prostate Cancer (TOPARP) study, which enrolled 50 mCRPC patients who received prior docetaxel (100%), abiraterone or enzalutamide (98%), and cabazitaxel (58%), olaparib demonstrated an ORR of 33% in 49 evaluable patients. Response was defined as any of the following: response according to RECIST version 1.1; at least 50% reduction in PSA level; or a confirmed reduction in the circulating tumor-cell count from 5 or more cells per 7.5 mL of blood to less than 5 cells per 7.5 mL. The ORR in patients with a mutation in a DNA repair gene (n = 16) was 88%, including 7/7 patients with a BRCA2 mutation and 4/5 patients with an ATM mutation. Median rPFS and OS in patients classified as biomarker positive (with HRR gene mutation) were 9.8 months and 13.8 months, respectively, compared to 2.7 months and 7.5 months for patient classified as biomarker negative (no HRR gene mutation).

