12.1 Adverse Events

Adverse events will be classified using the Medical Dictionary for Regulatory Activities (MedDRA) classification system. The severity of the toxicities will be graded according to the NCI CTCAE version 4.03 or higher whenever possible. Treatment-emergent adverse events (TEAEs) are defined as AEs with onset date on or after the date of first dose of study medication until the date of the last study medication dose plus 28 days. Adverse events will be considered treatment-emergent if all or part of the date of onset of the adverse event is missing and it cannot be determined if the adverse event meets the definition for treatment-emergent.

The number and percentage of patients who experienced TEAEs for each system organ class and preferred term will be presented. Multiple instances of the TEAE in each system organ class and multiple occurrences of the same preferred term are counted only once per patient. The number and percentage of patients with at least one TEAE will also be summarized.

MedDRA preferred terms will also be combined and presented in summaries for the following similar terms:

- Asthenia/Fatigue;
- ALT/AST Increased;
- Anemia and/or Decreased Hemoglobin;
- Thrombocytopenia and/or Decreased Platelets; and
- Neutropenia and/or Decreased ANC.

Separate tables will be presented as follows:

- TEAE Overview;
- All TEAEs;
- Treatment-related TEAEs;
- Grade 3 or higher TEAEs;
- Grade 3 or higher treatment-related TEAEs;
- Serious TEAEs;
- Serious treatment-related TEAEs;
- TEAEs by CTCAE grade;

- Treatment-related TEAEs by CTCAE grade;
- TEAEs with an outcome of death;
- Treatment-related TEAEs with an outcome of death;
- TEAEs leading to discontinuation of study medication;
- Treatment-related TEAEs leading to discontinuation of study medication;
- TEAEs leading to reduction of study medication;
- Treatment-related TEAEs leading to reduction of study medication;
- TEAEs resulting in interruption of study medication;
- Treatment-related TEAEs resulting in interruption of study medication;
- TEAEs resulting in reduction or interruption of study medication;
- Treatment-related TEAEs resulting in reduction or interruption of study medication;
- TEAEs resulting in reduction or interruption or discontinuation of study medication; and
- Treatment-related TEAEs resulting in reduction or interruption or discontinuation of study medication.

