The incidence of TEAEs will be summarized by relationship to study drug according to the following categories: “treatment-related,” or “not treatment-related”. If a patient experiences multiple occurrences of the same AE with different relationship categories, the patient will be counted once, as a relationship category of treatment related.

If a patient experiences multiple occurrences of the same AE with different toxicity grades, the patient will be counted once for the maximum (most severe) toxicity grade. AEs with a missing toxicity grade will be presented in the summary table with a toxicity grade of “Missing.” For each toxicity grade, the number and percentage of patients with at least one TEAE of the given grade will be summarized.

Time to the first treatment-related TEAE that resulted in a dose reduction, interruption, or discontinuation of study drug is defined as 1+ the number of days from the first dose of study drug to the start of the first respective AE. The cumulative incidence will be presented in a Kaplan-Meier plot for just the patients with an event, and the median time to onset will be calculated along with the 95% CI. Additionally, the analysis of combined terms for anemia will be presented as a time to first event analysis, as described above.

Non-TEAEs (pre-treatment and post-treatment) will be presented in the by-patient data listings for the safety population.

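### No planned adverse-event analysis separates event risk from time on drug, so by-group safety tables may make longer-treated groups look more toxic at the same risk

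*SAP*

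**What the plan says.** SAP section 12 sets the layout of the safety output: "In general, safety analyses will be presented by gene mutation (e.g., BRCA1/2, ATM, CDK12, CHEK2, and Other) and Overall". Safety is also to be explored by age group and race. The measurable-disease split is optional: "Safety data may also be presented by measurable disease status at baseline to explore the safety profile".

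SAP section 12.1 gives the summary measure: "The number and percentage of patients who experienced TEAEs for each system organ class and preferred term will be presented". Each patient counts once per term. An event is treatment-emergent if its onset falls between first dose and a limit that moves with treatment, "until the date of the last study medication dose plus 28 days".

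Section 12.1 also plans two time-to-onset analyses. One is "Time to the first treatment-related TEAE that resulted in a dose reduction, interruption, or discontinuation of study drug"; the other is the combined anemia terms, handled the same way. Both come with a median and 95% confidence interval, but with this restriction: "The cumulative incidence will be presented in a Kaplan-Meier plot for just the patients with an event".

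SAP section 8 summarises treatment duration without linking it to the adverse-event tables. Under SAP section 2.2, rucaparib continues until investigator-assessed progression or another reason for stopping, and may continue beyond progression by agreement. Neither document plans a person-time rate or an incidence within a fixed window.

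**The concern.** A percentage of patients with an event over the whole on-treatment period combines how likely the event is per unit of time with how long patients were watched. Here the length of observation is partly an efficacy result: a group whose disease is controlled for longer contributes longer windows. If the gene groups differ in benefit, which the sub-cohort futility rules and the gene-by-gene rule in Cohort C allow for, their windows will probably differ too.

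At stake is the reading that the layout invites. The stated aim of the measurable-disease split is "to explore the safety profile between patients with and without measurable disease at baseline", and the gene groups stand side by side. A group that benefits more could appear to tolerate the drug worse, and a group that stops early could appear to tolerate it better, with no difference in underlying risk.

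**Working it through.** The plan gives no rate or sample size for the between-group safety presentation, so there is no design figure to reproduce. The check has three parts.

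**1. Size of the distortion in crude percentages**

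Inputs, from Protocol section 3.4.2.3 (pooled ovarian treatment studies): Grade 3 or higher anemia in 132/545 = 24.2%; median treatment 160 days = 160/30.44 = 5.26 months. The 28-day tail in SAP 12.1 adds 28/30.44 = 0.92 months.

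Assumptions: the same constant hazard h in both groups; every patient treated for the group's median duration.

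- h = −ln(1 − 0.2422) / (5.26 + 0.92) = 0.2773 / 6.18 = 0.0449 per month.
- Crude incidence at m months on drug = 1 − exp(−h × (m + 0.92)).

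| Months on drug | Ratio to reference | h × window | Crude incidence |
|---|---|---|---|
| 4 | 1 | 0.0449 × 4.92 = 0.221 | 19.8% |
| 6 | 1.5 | 0.0449 × 6.92 = 0.311 | 26.7% |
| 8 | 2 | 0.0449 × 8.92 = 0.400 | 33.0% |

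The 4-month reference and the ratios are assumptions, because the documents report no time on drug by group.

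Counter-case: if all risk falls within the first 2 months and every group is treated for longer than that, crude incidence is 24.2% in each group and nothing is distorted.

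**2. Whether the planned time-to-event analyses repair this**

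With event-free patients left out, everyone plotted has the event, so the curve ends at 100% in every group. The median onset t among events solves 1 − exp(−h·t) = half the crude incidence:

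- 4 months on drug: t = −ln(1 − 0.099)/0.0449 = 2.3 months.
- 8 months on drug: t = −ln(1 − 0.165)/0.0449 = 4.0 months.

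The hazard is identical, yet onset looks later in the longer-treated group. The statistic is itself driven by exposure. It cannot correct the percentages, and it points the other way.

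**3. Whether an exposure-adjusted rate repairs it**

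The rate is patients with a first event divided by patient-time to first event or end of window. Under a constant hazard the expected patient-time per patient is (crude incidence)/h:

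- 4 months: 0.198 / 4.41 = 0.045 per month.
- 8 months: 0.330 / 7.35 = 0.045 per month.

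The rate recovers the common hazard. It fails when risk is front-loaded. Suppose both groups have 24.2% incidence with mean onset at 1 month:

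- 4 months: 0.242 / (0.242 × 1 + 0.758 × 4.92) = 0.061 per month.
- 8 months: 0.242 / (0.242 × 1 + 0.758 × 8.92) = 0.035 per month.

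The percentages agree, and the rates differ about 1.8-fold for no real reason. Neither measure is safe alone.

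**The case against.** The strongest reply is that this is descriptive reporting in a single-arm trial. No between-group safety test, hypothesis or decision rule is planned, and the measurable-disease split is optional. That stands, and it limits how much depends on the point. It does not supply a measure that separates risk from exposure.

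Three stronger readings are tempting, and the documents do not support them.

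- A reader might infer that the SAP offers percentages only. It does not: section 12.1 has the two time-to-onset analyses and section 8 reports duration. The defect is that the time-to-onset analyses leave out event-free patients.
- A reader might infer a several-fold difference in exposure from Protocol section 3.5, where median rPFS and OS in biomarker-positive and biomarker-negative patients "were 9.8 months and 13.8 months, respectively, compared to 2.7 months and 7.5 months". The contrast of 9.8 with 2.7 months is rPFS rather than time on drug, it concerns another PARP inhibitor, and its short arm is patients without an HRR mutation, who cannot enrol here.
- A reader might infer that longer-treated groups will look more toxic. In Protocol section 3.4.2.3, the sponsor's maintenance study had longer median treatment (8.3 versus 5.3 months) but less Grade 3 or higher anemia (18.8% versus 24.2%). The settings differ, so this does not disprove the bias, but it rules out certainty. The same section describes creatinine rises that appear early and then stabilise; events of that kind would be little affected.

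Efficacy is also not the only thing that sets time on drug. Toxicity and withdrawal end treatment, and treatment beyond progression extends it.

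**Conclusion.** The point holds as a reporting weakness. By-group percentages are taken over windows that vary with time on drug, and nothing else planned in section 12 separates risk from exposure, because the time-to-event analyses exclude event-free patients.

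For events with persisting risk, the distortion is about 7 percentage points at 1.5-fold exposure (26.7 − 19.8 = 6.9) and about 13 at 2-fold (33.0 − 19.8 = 13.2). For events confined to early treatment it is nil. These figures assume a constant hazard, an anchor from ovarian cancer patients, a 4-month reference group and exposure ratios that the documents do not report. They show what could happen, not what these groups will show.

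It does not follow that every between-group statement should rest on person-time rates. For front-loaded events those rates can mislead in the opposite direction.

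**What to change.** In SAP sections 12 and 12.1:

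1. In the main by-group TEAE tables (all, Grade 3 or higher, serious, treatment-related, and the combined anemia term), add the exposure-adjusted incidence rate with 95% confidence interval beside the crude percentage. The rate is patients with a first event divided by total patient-time from first dose to first event or to last dose plus 28 days. Show treatment duration for each group in the same table.
2. Run both time-to-first-event analyses in all treated patients, censoring event-free patients at last dose plus 28 days, and report cumulative incidence at fixed times.
3. State that rates, fixed-time incidence and crude percentages are to be read together.

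The cost is SAP wording and programming; onset and dosing dates are already collected. The downside is that the rate assumes a roughly constant hazard, can mislead for early-onset events, and will be imprecise in small gene groups, since fewer than 6 patients per gene are anticipated in Cohort C.

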12.1 Adverse Events

Adverse events will be classified using the Medical Dictionary for Regulatory Activities (MedDRA) classification system. The severity of the toxicities will be graded according to the NCI CTCAE version 4.03 or higher whenever possible. Treatment-emergent adverse events (TEAEs) are defined as AEs with onset date on or after the date of first dose of study medication until the date of the last study medication dose plus 28 days. Adverse events will be considered treatment-emergent if all or part of the date of onset of the adverse event is missing and it cannot be determined if the adverse event meets the definition for treatment-emergent.

The number and percentage of patients who experienced TEAEs for each system organ class and preferred term will be presented. Multiple instances of the TEAE in each system organ class and multiple occurrences of the same preferred term are counted only once per patient. The number and percentage of patients with at least one TEAE will also be summarized.

MedDRA preferred terms will also be combined and presented in summaries for the following similar terms:

- Asthenia/Fatigue;
- ALT/AST Increased;
- Anemia and/or Decreased Hemoglobin;
- Thrombocytopenia and/or Decreased Platelets; and
- Neutropenia and/or Decreased ANC.

Separate tables will be presented as follows:

- TEAE Overview;
- All TEAEs;
- Treatment-related TEAEs;
- Grade 3 or higher TEAEs;
- Grade 3 or higher treatment-related TEAEs;
- Serious TEAEs;
- Serious treatment-related TEAEs;
- TEAEs by CTCAE grade;

- Treatment-related TEAEs by CTCAE grade;
- TEAEs with an outcome of death;
- Treatment-related TEAEs with an outcome of death;
- TEAEs leading to discontinuation of study medication;
- Treatment-related TEAEs leading to discontinuation of study medication;
- TEAEs leading to reduction of study medication;
- Treatment-related TEAEs leading to reduction of study medication;
- TEAEs resulting in interruption of study medication;
- Treatment-related TEAEs resulting in interruption of study medication;
- TEAEs resulting in reduction or interruption of study medication;
- Treatment-related TEAEs resulting in reduction or interruption of study medication;
- TEAEs resulting in reduction or interruption or discontinuation of study medication; and
- Treatment-related TEAEs resulting in reduction or interruption or discontinuation of study medication.

The incidence of TEAEs will be summarized by relationship to study drug according to the following categories: “treatment-related,” or “not treatment-related”. If a patient experiences multiple occurrences of the same AE with different relationship categories, the patient will be counted once, as a relationship category of treatment related.

If a patient experiences multiple occurrences of the same AE with different toxicity grades, the patient will be counted once for the maximum (most severe) toxicity grade. AEs with a missing toxicity grade will be presented in the summary table with a toxicity grade of “Missing.” For each toxicity grade, the number and percentage of patients with at least one TEAE of the given grade will be summarized.

Time to the first treatment-related TEAE that resulted in a dose reduction, interruption, or discontinuation of study drug is defined as 1+ the number of days from the first dose of study drug to the start of the first respective AE. The cumulative incidence will be presented in a Kaplan-Meier plot for just the patients with an event, and the median time to onset will be calculated along with the 95% CI. Additionally, the analysis of combined terms for anemia will be presented as a time to first event analysis, as described above.

Non-TEAEs (pre-treatment and post-treatment) will be presented in the by-patient data listings for the safety population.

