Confirmed PSA response is defined as $\geq 50\%$ reduction in PSA from baseline to lowest post-baseline PSA result, with a consecutive assessment conducted at least 3 weeks later. PSA response will be calculated for all patients with PSA values at baseline and at least 1 post-baseline assessment. PSA will be assessed by a local laboratory.

Time to PSA progression is defined as the time from first dose of rucaparib to the date that a $\geq 25\%$ increase and absolute increase of ≥ 2 ng/mL above the nadir (or baseline value for patients who did not have a decline in PSA) in PSA was measured. The increase must be confirmed by a second consecutive assessment conducted at least 3 weeks later.

Safety Analyses

Adverse events (AEs), clinical laboratory results, vital signs, ECOG performance status, body weight, and concomitant medications/ procedures will be tabulated and summarized. AEs will be summarized overall and separately for SAEs, AESIs, AEs leading to discontinuation, AEs leading to death, and Grade 3 or higher AEs graded using National Cancer Institute Common Terminology Criteria for Adverse Events (CTCAE) Version 4.03 or higher. Body weight and vital signs will be summarized descriptively (N, mean, standard deviation, median, minimum, and maximum). ECOG performance status will be summarized categorically.

A DMC will review safety and efficacy data on a periodic basis to ensure an acceptable overall risk and benefit for patients participating in the study.

Date of Protocol Amendment 4 Approval

24 August 2020

TABLE OF CONTENTS

1	SYNOPSIS.....	4
	LIST OF IN-TEXT TABLES	23
	LIST OF IN-TEXT FIGURES.....	23
2	LIST OF ABBREVIATIONS AND DEFINITIONS OF TERMS.....	24
3	INTRODUCTION	29
3.1	Investigational Product	29
3.2	Background and Rationale for PARP Inhibition	29
3.3	Metastatic Castration-resistant Prostate Cancer.....	29
3.3.1	Treatment of Metastatic Castration-resistant Prostate Cancer.....	30
3.4	Prior Experience with Rucaparib	31
3.4.1	Nonclinical Experience with Rucaparib	31
3.4.2	Clinical Experience with Rucaparib	32
3.5	Rationale for this Study of Rucaparib.....	41
4	STUDY OBJECTIVES.....	44
4.1	Primary Objective	44
4.2	Secondary Objectives.....	44
4.3	Exploratory Objectives	44
5	INVESTIGATIONAL PLAN.....	46
5.1	Overall Study Design and Plan	46
5.1.1	Pre-Screening Phase.....	46
5.1.2	Screening Phase	47
5.1.3	Treatment Phase.....	47
5.1.4	Post-treatment Phase.....	48
5.2	Study Schema.....	49
5.3	End of Study	52
6	STUDY POPULATION SELECTION	53

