Myelodysplastic syndrome (MDS) and acute myeloid leukemia (AML) are considered adverse events of special interest (AESI), as these events have been observed in patients exposed to cytotoxic chemotherapy (eg, platinum and anthracyclines) used for treatment of ovarian cancer as well as with PARP inhibitors, including rucaparib. Patients in rucaparib clinical studies diagnosed with MDS or AML had significant confounding risk factors including prior cytotoxic chemotherapy, and in some cases a deleterious BRCA mutation, which increases the risk of developing cancer(s). Based on these confounding factors, there is insufficient scientific evidence to conclude that MDS and AML are causally related to rucaparib. More information on

AESIs of MDS/AML experienced by patients in rucaparib clinical studies is provided in the rucaparib IB.

Adverse events (AEs) of pneumonitis have been reported with PARP inhibitor treatment, including in clinical trials evaluating rucaparib. Currently, however, there is a lack of understanding of a mechanistic link between pneumonitis and PARP inhibitor treatment, and causality assessment is often confounded by lack of a consistent clinical pattern as well as other pre-disposing factors, such as cancer and/or metastases in lungs, underlying pulmonary disease, smoking history, and/or previous chemotherapy and radiotherapy. Clovis is seeking to understand whether or not there is a relationship between pneumonitis and rucaparib treatment; thus, Clovis is designating pneumonitis as an AESI to gather data to enable a thorough evaluation and assessment of the event and associated terms specified in [Section 10.7](#). Also, refer to the rucaparib IB for information regarding the AESI of pneumonitis.

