5.1.4 Post-treatment Phase

The sponsor (or designee) should be notified of all treatment terminations as soon as possible. The date and reason for cessation of study drug must be documented in the eCRF and source documents. Patients will undergo procedures and assessments during the Post-treatment Phase as described in [Section 9.6](#). Upon treatment discontinuation, patients will have a Treatment Discontinuation Visit ([Section 9.6.1](#)), a 28-Day Follow-up Visit ([Section 9.6.2](#)), and then will proceed to long-term follow-up ([Section 9.6.3](#)). An optional tumor biopsy will be collected prior to the start of subsequent anticancer therapy from patients who experience radiographic or unequivocal clinical disease progression and who provide appropriate consent. For patients who had their last tumor assessment ≥ 8 weeks (≥ 12 weeks if previous scan was after 24 weeks on study) prior to Treatment Discontinuation Visit, a tumor assessment must be performed.

If treatment was discontinued for reasons other than radiologic disease progression, radiologic tumor assessment (using the same methodology as was used at initial study screening [eg, CT scan]) and PRO assessments will continue until confirmed radiographic disease progression. For these patients, tumor assessments should continue to be performed at the end of every 8 calendar weeks (± 7 days) relative to Study Day 1 (Week 1) up to 24 weeks and then every 12 calendar weeks (± 7 days) thereafter, until confirmed radiologic disease progression by modified RECIST Version 1.1 and PCWG3 (for bone lesions only) criteria as assessed by the investigator, loss to follow-up, withdrawal of consent, or study closure. For patients who start subsequent

anticancer therapy, tumor assessments will continue until radiologic disease progression is confirmed.

Ongoing SAEs, AESIs, and treatment related Grade 3/4 AEs will be followed until either resolution or stabilization has been determined or until loss to follow-up. After the 28-Day Follow-up Visit, only SAEs considered as potentially related to study drug should be reported per Clovis Pharmacovigilance (PV) requirements and captured in the Clovis PV database. This includes serious reports of pneumonitis or associated events, if considered to be related to study drug.

After the 28-day Follow-up Visit, AESIs of MDS and AML, irrespective of causality, should be reported per Clovis PV requirements and captured in the Clovis PV database.

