9 STUDY PROCEDURES AND ACTIVITIES BY VISIT

9.1 Schedule of Assessments

[Table 5](#) summarizes the procedures and assessments to be performed for all patients. Study procedures and assessments should be performed as close to the scheduled time as possible, but within ± 3 days of the scheduled time unless otherwise stated.

Table 5. Schedule of Assessments

Procedure ^a	Pre-screening Phase	Screening Phase		Treatment Phase					Post-Treatment Phase		
				Week 1	Week 3	Week 5	Week 7	Week 9 & every 4 weeks thereafter			
		Day -28 to Day -1	Day -14 to Day -1	Study Day 1 ^b	Study Day 15	Study Day 29	Study Day 43	Day 57 & every 28 days thereafter	Treatment Discontinuation	28-day Follow-up	Long-term Follow-up
Informed Consent	X ^c	X									
BRCA, ATM or other HRR gene mutation assessment from ctDNA blood and tumor sample ^{c, d}	X ^c										
Medical/Oncology History ^e		X									
Blood samples for plasma ctDNA analysis ^f		X		X		X		X	X		
Physical Examination, Weight, Height ^g		X		X	X	X	X	X	X	X	
Vital Signs ^h		X		X	X	X	X	X	X	X	
12-lead ECG ⁱ		X							X		
Prior/Concomitant Medications/Procedures		X		X	X	X	X	X	X	X	
Tumor Assessment/CT/MRI and Bone Scan ^j		X		End of every 8 weeks from Study Day 1, up to 24 weeks (Study Weeks 9, 17, 25) and then every 12 weeks thereafter (Study weeks 37, 49, 61, etc.) ^k					X ^l	X ^l	X ^l
Archival Primary/ Metastatic Tumor Tissue Sample for retrospective testing ^m		X									
Patient-reported outcome (BPI-SF, analgesic drug score, FACT-P, EQ-5D-5L) ⁿ			X	X		X		X	X	X	X
ECOG Performance Status			X	X	X	X	X	X	X	X	
Serum Testosterone		X									
PSA Measurement ^o		X		X		X		X	X		
Clinical Laboratory Assessments ^p			X	X	X	X	X	X	X	X	
Pharmacogenomic blood sample ^q				X							
Study Drug Dispensation				X		X		X			
Adverse Events ^r	(X)	(X)	(X)	X	X	X	X	X	X ^s	X ^s	
Plasma PK Sample						X ^t		X ^t			

Post-progression Tumor Biopsy (Optional)										X ^u		
Subsequent Treatments, AESIs, & Survival ^v											X	X

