9.6.3 Long-term Follow-up

Patients who complete a 28-Day Follow-up Visit after the last dose of rucaparib will continue in long-term follow-up as described below.

- If applicable, tumor assessment (using the same methodology as was used at initial study screening [eg, CT scan]) when the reason for treatment discontinuation was other than death or disease progression based on radiologic assessment and it has been ≥ 8 weeks (≥ 12 weeks if previous scan was after 24 weeks on study) since last scan or disease progression was noted on the last scan. Tumor assessment should continue to be performed at the end of every 8 calendar weeks (± 7 days) relative to Study Day 1 (Week 1) up to 24 weeks, then every 12 calendar weeks (± 7 days), until confirmed radiologic disease progression by modified RECIST Version 1.1 and/or PCWG3 (for bone lesions only) criteria, as assessed by the investigator, loss to follow-up, withdrawal, or study closure.
 - PRO assessments will also continue and coincide on days when tumor assessments are performed until confirmed radiographic disease progression. PRO using the BPI-SF ([Appendix 6](#)), FACT-P ([Appendix 7](#)), EQ-5D-5L ([Appendix 8](#)), and analgesic drug score instruments ([Appendix 9](#))
- All patients discontinued from treatment, regardless of reason, will be followed and information collected for subsequent treatments and survival every 12 weeks from last dose of rucaparib until death, loss to follow-up, withdrawal of consent from study, or closure of the study. Follow-up can be performed via the telephone and can be completed to coincide with scheduled tumor assessments and/or PRO during this period.
- SAEs related to study drug and AESIs are to be reported as specified in [Section 10.7](#).

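### The protocol synopsis promises an AESI summary that neither Protocol 11.6.1 nor SAP 12.1 lists, and MDS/AML with a known onset more than 28 days after last dose enters no summary table

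*SAP*

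**What the plan says.** **Promise.** The Safety Analyses paragraph of the protocol synopsis states that "AEs will be summarized overall and separately for SAEs, AESIs, AEs leading to discontinuation, AEs leading to death, and Grade 3 or higher AEs" will be tabulated. Protocol 3.4.2.3 names MDS, AML and pneumonitis as AESIs, and Protocol 10.7 lists eight pneumonitis-type terms to be reported as such.

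**Collection.** Protocol 5.1.4 says: "After the 28-day Follow-up Visit, AESIs of MDS and AML, irrespective of causality, should be reported per Clovis PV requirements". Sections 9.10.1, 10.7 and 10.8 repeat the duty, and the schedule of assessments (Protocol 9.1) has a post-treatment row headed "Subsequent Treatments, AESIs, & Survival". Under Protocol 10.7 the AE case report form covers events up to 28 days after the last dose. Later MDS/AML reports go to the sponsor's pharmacovigilance database.

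**Analysis.** SAP 12.1 ends the treatment-emergent period at the same point, "until the date of the last study medication dose plus 28 days", and lists 21 tables, all of treatment-emergent events. For everything outside the window it says: "Non-TEAEs (pre-treatment and post-treatment) will be presented in the by-patient data listings for the safety population". Protocol 11.6.1 uses the same window and lists nine tables, none for AESIs. It also says that treatment-emergent events are the only ones to be collected.

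**Declared changes.** SAP Section 13 covers PSA response, PSA progression, clinical benefit rate, a PSA waterfall plot and the CTCAE version for laboratory grading. It does not mention AESIs.

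**The concern.** MDS/AML has the widest late-reporting rule in this protocol. After the 28-day visit, other serious events are reported only if potentially drug-related, and pneumonitis stops being reported as an AESI. MDS and AML alone continue irrespective of causality. That extension has analytic value only if the late cases are counted somewhere.

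As the plan stands, a person reading the safety tables could find few or no MDS/AML cases, with nothing to show that the tables stop at 28 days while collection does not. A listing gives neither a count over a denominator nor a follow-up time. Within the window the AESIs are scattered by preferred term: the five combined-term groups in SAP 12.1 cover neither MDS/AML nor the pneumonitis terms.

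**Working it through.** This is mainly a comparison of text.

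**Step 1: is the promised summary planned?** The synopsis names five separate summaries:

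| Synopsis category | Table in SAP 12.1 | Table in Protocol 11.6.1 |
|---|---|---|
| Serious events | yes | yes |
| AESIs | **none of 21** | **none of 9** |
| Leading to discontinuation | yes | yes |
| Leading to death | yes | yes |
| Grade 3 or higher | yes | yes |

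Four of the five are carried through. AESIs are not, and the SAP's abbreviation list does not contain the term.

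**Step 2: where does an MDS/AML case go?**

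- *Onset within 28 days of last dose:* the ordinary treatment-emergent tables, by preferred term, not grouped as an AESI.
- *Diagnosed later, but with attributed signs or symptoms that began inside the window:* Protocol 10.7.1 dates onset from those signs or symptoms, so the case can count as treatment-emergent.
- *Missing or partial onset date that leaves the status undeterminable:* counted as treatment-emergent under SAP 12.1.
- *Known onset after 28 days:* no summary table. It belongs in the listing of non-treatment-emergent events, but the AE case report form has closed and the report sits in the pharmacovigilance database. The SAP does not say that this database feeds, or is reconciled with, the analysis data.

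The gap is the last group.

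**Step 3: what could it amount to?** The documents give no count of late cases, so this step only illustrates. Planned enrollment is 150 + 150 + 60 = 360. The two-sided 95% Clopper-Pearson upper limit for x of n is the value of p that solves P(X ≤ x | n, p) = 0.025. For x = 0 this is 1 − 0.025^(1/360) = 1.0%.

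| Late cases (assumed) | Rate in 360 | Upper 95% limit |
|---|---|---|
| 0 | 0% | 1.0% |
| 1 | 1/360 = 0.3% | 1.5% |
| 3 | 3/360 = 0.8% | 2.4% |
| 5 | 5/360 = 1.4% | 3.2% |

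If every case had a known late onset, the tables would show the first row whichever row was true. The 360 is built from upper enrollment limits, and Cohorts B and C stop when Cohort A (BRCA1/2) is full, so the actual denominator may be smaller.

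**The case against.** **The SAP is not out of line with the protocol's statistical section.** A reader might infer that the SAP dropped something the protocol had settled. The documents do not support that. Protocol 11.6.1 has no AESI table and uses the same window, so the SAP follows the body of the protocol and the protocol disagrees with its own synopsis. This stands. It moves part of the correction into the protocol, but the AESI summary remains promised and unplanned.

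**No summary beyond 28 days is promised.** A reader might also infer a broken commitment on late MDS/AML. The post-treatment text sets reporting duties, not analyses, and the 28-day window is consistent across both documents. This stands too: counting late cases is a recommendation, resting on the fact that the protocol chose to collect them.

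**Late cases are not invisible.** They may be listed, individual cases still reach the sponsor, and some late diagnoses can carry an in-window onset. All true. The point is therefore limited to cases with a known late onset and to summary tables.

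**A treatment-emergent count does not claim to be cumulative incidence.** Correct; it misleads only if read as one. With no other MDS/AML summary planned, that misreading is easy.

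**A crude percentage over all follow-up has its own flaw.** Under Protocol 5.3 the study may close once every patient has stopped treatment and completed the 28-day visit, so patients who stop late may contribute almost no later observation. This stands, and the fix allows for it.

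**Conclusion.** The point holds in this form. The synopsis promises an AESI summary, both lists of planned tables lack one, and the omission is undeclared. Under the stated window and listing rule, MDS/AML with a known onset more than 28 days after last dose enters no summary table, and reaches a listing only if pharmacovigilance data are brought into the analysis data.

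The size is unknown. The figures for 1, 3 and 5 late cases rest on assumed counts, a denominator of 360 and all cases falling outside the window; they are not an estimate. A reader might infer that late MDS/AML goes wholly unreported or that the tables will show zero. Neither follows, because of the listing, the symptom-based onset date and the missing-date rule.

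No efficacy analysis or primary conclusion changes. The plan should be corrected because a count of a named special-interest risk would otherwise be incomplete, and the data needed are already required.

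**What to change.** 1. Add to SAP 12.1 an AESI table covering MDS, AML, pneumonitis and the associated terms in Protocol 10.7.
2. For MDS/AML, also report the number and percentage of the safety population with onset at any time after first dose, split into within and after 28 days of last dose. Show the length of post-treatment follow-up beside it, so that the later figure is not read as if everyone had been observed equally.
3. State in the SAP that MDS/AML cases in the pharmacovigilance database are reconciled into the analysis data, for the new table and for the listing of post-treatment events.
4. Align Protocol 11.6.1 with the synopsis by adding the AESI summary, and reconcile its statement that treatment-emergent events are the only ones collected with the late-reporting rule in Protocol 10.7.

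The cost is one or two descriptive tables, one database reconciliation and a wording correction in the protocol. No new patient procedure is needed. Reported MDS/AML incidence may come out slightly higher.
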